3.2.5 Patient Characteristics

Disposition and Analysis Population

The number of patients screened, randomized, dosed, number of patients included in each analysis set, the number of patients who completed treatment, discontinued treatment along with reasons for discontinuing treatment, entered post-treatment follow-up, completed post-treatment follow-up, and discontinued post-treatment follow-up, along with reasons for early terminating post-treatment follow-up, will be presented in screened patients by treatment group to which they were randomized, and overall.

Listings of patient disposition will also be provided for all randomized patients.

Protocol Deviation

Major protocol deviations will be summarized by deviation category for randomized patients. Reasons for excluding patients from PPS will be summarized for randomized patients. All protocol deviations (major and minor) will be provided in a data listing for randomized patients.

Demographic and Baseline Characteristics

Demographic and baseline characteristics will be summarized by treatment group and overall in FAS, including age, sex, race, ethnicity. Baseline characteristics include number of patients with established CVD vs. high risk for CVD, weight, height, body mass index (BMI), triglycerides, apoA-I, apoB, apoC-III, TC, LDL-C, HDL-C, non-HDL-C, VLDL-C, ANGPTL3, remnant cholesterol, and Lp(a).

Medical History

Medical history will be coded by Medical Dictionary for Regulatory Activities (MedDRA) dictionary Version 20.1 and will be summarized by System Organ Class (SOC) and Preferred Term (PT) by treatment group and overall for the FAS. Medical history will also be provided in a data listing.

Cardiovascular history will be tabulated by ISIS 678354 treatment group and pooled placebo group. A by-patient data listing will also be provided.

Prior/Concomitant Medications

All medications will be coded by World Health Organization Drug Dictionary (WHODD) Version DEC2017. The start and stop dates of medications that are recorded on the Concomitant Medications CRF will be used to determine whether the medications are prior or concomitant to the treatment period. Missing or partial dates will be imputed as outlined in Section 3.7.1. Prior medications include medications that started prior to the first dose of Study Drug from the time the patient has signed the informed consent, regardless whether continued while on treatment or not. A concomitant medication is any drug or substance (including over-the-counter (OTC) medications, herbal medications and vitamin supplements) administered between first administration of study drug and the end of the post-treatment follow-up period. A prior medication with an imputed stop date that is missing or on or after date of first dose of Study Drug will also be considered as a concomitant medication. Medications will be classified based on imputed start and imputed stop dates as follows:

1) Prior Medication

Start Date	End Date
< FDD	≥ Inform Consent Date
	Missing

FDD = Date of First Dose of Study Drug

2) Concomitant Medication

Start Date	End Date
< FDD	\geq FDD
	Missing
\geq FDD	Any non-missing stop date
	Missing

FDD = Date of First Dose of Study Drug

Prior or concomitant medications will be summarized separately for all Safety Set by Anatomical Therapeutic Chemical (ATC) class, Preferred Term, treatment group and overall with counts and percentages, sorting by decreasing frequency of all patients. The concomitant medications in on-treatment and on-study period will be summarized respectively.

Prior or concomitant medications will be displayed in patient listings for all Randomized Patients. A listing of ancillary procedures will also be provided. Note that imputed dates will be used for prior and concomitant medications classification. Originally reported dates will be used for listings.

Treatment Exposure and Compliance

Treatment duration and amount of Study Drug received will be summarized by treatment group and overall in Safety Set. Compliance to Study Drug will be summarized by descriptive statistics by treatment group and overall.

Compliance (%) will be calculated as follows:

$100 \times (\text{total volume of Study Drug}) / (\text{total volume of Study Drug scheduled during the treatment period})$.

For early withdrawals/terminations, the volume of Study Drug will be calculated for the period up to their withdrawal/termination.

3.3 Primary Analyses

3.3.1 Primary Endpoint Definition

The primary endpoint is the percent change in fasting triglycerides from baseline to the primary analysis time point. The primary analysis time point is Week 25 for patients in Cohort A and B, and Week 27 for Cohort C and D.

3.3.2 Primary Efficacy Analysis

The primary efficacy analysis for the primary endpoint will be the pairwise comparison of percent change from baseline to the primary analysis time point in fasting triglycerides between ISIS 678354 treated groups and pooled placebo group in the FAS.

The percent change from baseline in triglycerides will be analyzed using an ANCOVA model with treatment group as a fixed factor and log-transformed baseline triglycerides as a covariate. The ANCOVA model will use $\log(Y/X)$ as dependent variable, where Y is the post-baseline value of triglycerides and X is the baseline value of the triglyceride. The model will provide an estimate of the log ratio, which will then be converted back to the original ratio scale. The percent change from baseline will then be estimated based on the estimated ratio. Patients with missing primary endpoint will have their fasting triglyceride value imputed using the multiple imputation method described below.

Missing data for the primary efficacy endpoint will be handled by a multiple imputation model that contains the following variables: log-transformed baseline fasting triglyceride value, log-transformed fasting post-baseline triglyceride values, stratified by treatment ([Schafer 1997](#); [Schafer 1999](#)). Imputation of missing data will be conducted under a working assumption of missing at random (MAR), meaning that the propensity for a data point to be missing is not related to the missing data, but it is related to some of the observed data.

The imputations will be performed for post-baseline visits. The Markov Chain Monte Carlo (MCMC) method will be used under the multivariate normality assumption to impute the missing primary endpoint by treatment group (ISIS 678354 treatment group or pooled placebo treatment group). In order to be compliant with the normality assumption, baseline and post-baseline triglyceride data will be log-transformed prior to the imputation process and will be reverted when creating the imputed dataset. The MCMC method will impute 100 datasets in order to estimate the treatment effect, where the median value across the imputed datasets will be used for patients with missing endpoint.

The primary endpoint will be compared between each ISIS 678354 treatment group and the pooled placebo group for each of the 100 imputed datasets. The estimates from the 100 fitted models will be combined to provide an overall estimate, with corresponding CIs and p-value ([Little and Rubin, 2002](#)). Results from the ANCOVA model will be tabulated by ISIS 678354 treatment groups compared to the pooled placebo group.

For fasting triglycerides, observed value, change from baseline and percentage of change will be summarized by analysis visit using descriptive statistics in FAS.

Mean (SD) percent change over time in fasting triglycerides will be plotted by ISIS 678354 treatment group and pooled placebo group, until there are fewer than 10% of the FAS/PPS population at a given visit. Waterfall plots of by-patient percent changes from baseline to the primary analysis time point will also be provided.

The primary efficacy analysis will take place after the last patient has completed the primary analysis time point, and the database has been locked.

All primary efficacy data will be provided in data listings.

The sample SAS code for the ANCOVA model can be found below: where the baseline and post-baseline values will be log-transformed first. Log (post-baseline/baseline) calculated as log (post-baseline) – log (baseline) will be subjected to the ANCOVA model.

* Note:

* Base= baseline

* Y=Post-baseline

* TRTP = Treatment group: Pooled Placebo, 10 mg Q4W, 50 mg Q4W, 15 mg Q2W, 10 mg QW

ods output lsmeans=lsm diff=diff;

proc mixed data = dataset;

 class TRTP (ref='pooled placebo') ;

 model log (Y/base) = TRTP log(Base) /solution cl;

 lsmeans TRTP/ diff cl;

run;

3.3.3 *Sensitivity Analyses of Primary Endpoint*

In addition to the primary efficacy analysis, the following sensitivity analyses will be conducted on the FAS.

Sensitivity Analysis 1 (Per Protocol Set): The primary efficacy analysis will be repeated, using the PPS population.

Sensitivity Analysis 2 and 3 (Non-Parametric Analyses): The primary efficacy endpoint will be analyzed using a non-parametric Wilcoxon Rank Sum test using both the FAS and the PPS. Missing data will be handled using the same MCMC multiple imputation method as the primary analysis. The

treatment effect will be estimated using the Hodges-Lehmann estimator of the location shift between ISIS 678354 treatment groups and the pooled placebo group. Asymptotic 95% CI and corresponding p-values will be provided.

Sensitivity Analysis 4 (FAS) Using controlled imputations (pattern mixture models [PMM] with ANCOVA) will be conducted to assess the robustness of the missing at random assumption. With this approach, missing not at random (MNAR) is assumed, and the mean function for the missing data from patients treated with ISIS 678354 who discontinue the study is pre-specified. Missing triglycerides for placebo patients will be imputed using the same MCMC multiple imputation method as the primary analysis. Patients treated with ISIS 678354 who discontinue the study due to AE or lack of efficacy will have their post-discontinuation triglyceride values imputed using estimates from the placebo patients using the copy increment from reference (CIR) approach, detailed in ([Carpenter et al. 2013](#)). The assumption is based on the premise that when a patient discontinues treatment due to informative missing data, at the time of discontinuation they would progress in a similar manner as placebo-treated patients. Otherwise, non-informative missing data will be imputed using the same MCMC method as the primary analysis, since it is assumed that those patients would have continued in a similar manner to similar patients in their own treatment group who remained on the study. Therefore, the missing data for these patients is expected to be missing at random.

Sensitivity Analysis 5 (FAS) An ANCOVA will be performed on the primary efficacy endpoint without applying any imputation for missing data.

Sensitivity Analysis 6 (FAS) A repeated measures analyses will be performed on the fasting triglyceride endpoint. The percent change from baseline in triglycerides will be analyzed using an MMRM model with treatment group as a fixed factor, log-transformed baseline triglycerides and timepoint as covariates. If log transformation is applied, the analysis will carry the same conditions as the primary efficacy analysis for back transformation. No imputation of data is applied to this analysis. Analysis visits beyond PAT (Week 29, 37, 45, and 53) will be included only if the total n at the analysis visit is at least 10% of the overall FAS. Visit mapping is provided in [Appendix A](#) and SAS code is outlined in [Appendix B](#).

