10.6.3 Efficacy Analysis

10.6.3.1 Analysis of Primary Efficacy Endpoint

The primary efficacy analysis for the primary endpoint will be the pairwise comparison of percent change from Baseline to the primary analysis time point in fasting TG between ISIS 678354 treated groups and pooled placebo group in the FAS. The data will be analyzed using an ANCOVA model with the baseline TG level as a covariate. Missing data may be handled by LOCF or multiple imputation methods ([Schafer 1997](#), [Schafer 1999](#)).

The primary efficacy analysis will take place after the last patient has completed the primary analysis time point, and the database has been locked,

The following sensitivity analyses will be conducted:

- The primary analysis will be repeated in the PPS
- The primary efficacy endpoint will be analyzed using a Wilcoxon Rank Sum test on both FAS and PPS, and the treatment effect will be estimated using Hodges-Lehmann estimator

Additional sensitivity analyses may be conducted as appropriate; the details of these analyses will be outlined in the SAP.

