3 ANALYSIS PLANS

3.1 Statistical Design Summary

This is a multi-center, randomized, double blind, placebo-controlled study.

The study hypotheses will be formally evaluated at the planned EoT analysis on data obtained through the data cut-off date, defined as the date of the last EoT visit. The database will be queried, and data cleaning performed on all data, with database interim lock of all data, at which point the treatment code is unblinded and the EoT analysis is performed.

The primary analysis model will be an Analysis of Covariance (ANCOVA) model for percent change from baseline to the PAT in fasting triglycerides. Missing data will be imputed by a multiple imputation method as the primary analysis and will be supported by various sensitivity analyses.

The treatment groups proposed in this analysis are defined as follows:

- ISIS 678354 10 mg every 4 weeks (Q4W)
- ISIS 678354 50 mg every 4 weeks (Q4W)
- ISIS 678354 15 mg every 2 weeks (Q2W)
- ISIS 678354 10 mg every week (QW)
- Pooled Placebo, defined as the combined group of placebo patients from the 4 randomized cohorts

A final analysis will be performed after all data from the 13-week post treatment follow-up period are collected and locked.

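### SAP 3.3.2 gives two incompatible rules for the imputed primary endpoint: a single median per patient, or 100 pooled fits; the median rule would make standard errors too small

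*Combined protocol and SAP*

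**What the plan says.** SAP 3.1 names the primary missing-data method: "Missing data will be imputed by a multiple imputation method as the primary analysis". SAP 3.3.2 then describes MCMC imputation within treatment group on the log scale, under missing at random, with 100 datasets generated "in order to estimate the treatment effect, where the median value across the imputed datasets will be used for patients with missing endpoint".

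The paragraph that follows in SAP 3.3.2 compares each active group with pooled placebo in every imputed dataset and adds: "The estimates from the 100 fitted models will be combined to provide an overall estimate, with corresponding CIs and p-value". The same section plans one display that needs a single value per patient: "Waterfall plots of by-patient percent changes from baseline to the primary analysis time point will also be provided".

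The protocol does not decide between the rules. Section 10.6.3.1 says only: "Missing data may be handled by LOCF or multiple imputation methods".

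Several other analyses inherit the imputation:
- Sensitivity Analysis 1 (SAP 3.3.3): "The primary efficacy analysis will be repeated, using the PPS population".
- Sensitivity Analyses 2 and 3 (SAP 3.3.3), Wilcoxon and Hodges-Lehmann: "Missing data will be handled using the same MCMC multiple imputation method as the primary analysis".
- Sensitivity Analysis 4 (SAP 3.3.3), in part: "Missing triglycerides for placebo patients will be imputed using the same MCMC multiple imputation method as the primary analysis".
- The subgroup analyses (SAP 3.3.4) and the two triglyceride responder models (SAP 3.4 and Table 5).

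**The concern.** A median over imputations is one fixed number per patient. An ANCOVA on data filled this way treats that number as if it had been measured. The reported standard error then leaves out both the uncertainty about the missing value and the residual scatter a real observation would have had. Confidence intervals come out too narrow and the 5% test rejects too often.

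Two competent analysts following SAP 3.3.2 could therefore report different intervals and p-values for the primary endpoint. The risk is greater downstream. The combining step is written for fitted models, and Sensitivity Analyses 2 and 3 are rank-based with no combining rule stated. There, the median is the only written rule that yields a single analysable dataset.

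**Working it through.** **The two rules side by side.** For M = 100 imputations, Rubin's total variance is T = W + (1 + 1/M)B, where W is the average within-dataset variance and B the variance of the 100 estimates. If the median is inserted first, every dataset is the same, so B = 0 and T = W. W is itself too small, because the filled values carry no residual noise while the ANCOVA keeps its full 100 - 6 = 94 degrees of freedom.

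**Inputs from the documents.** About 100 patients; four cohorts of 25 randomized 4:1, so 20 per active arm and 4 x 5 = 20 pooled placebo (protocol synopsis; SAP 2.2 and 3.1). Baseline is the mean of two log-triglyceride values (averaging as in SAP 3.2.4, here on the log scale). Visits are Weeks 5, 9, 13, 17, 21 and the primary time point (SAP Appendix B). The model is log(Y/X) on treatment and log baseline, two-sided 5%.

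**Assumptions, because the documents give no figure.** Log-scale SD 0.40; equal between-visit correlation 0.5 or 0.7; exactly 1, 2 or 4 of 20 per arm missing completely at random (5%, 10%, 20%), either as dropout spread over visits or at the primary time point only. The SAP states no imputation prior, so two were used: a joint Jeffreys prior and a per-visit regression prior. Each of the 12 scenarios had 4,000 replicates with 4 contrasts. The plan has no readable figure to reproduce here.

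**Complete-data benchmark.** With correlation 0.5, baseline variance is 0.16 x 1.5/2 = 0.12 and its covariance with the endpoint is 0.08. Residual variance is 0.16 - 0.08²/0.12 = 0.1067. The standard error is about √(0.1067 x 2/20) = 0.103. With correlation 0.7 the same steps give 0.16 - 0.112²/0.136 = 0.0678 and about 0.082.

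**Standard errors, spread dropout.**

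| Correlation | Missing | Median fill | Pooled, joint prior | Pooled, per-visit prior | True SD |
|---|---|---|---|---|---|
| 0.5 | 5% | 0.1017 | 0.1084 | 0.1117 | 0.1059 |
| 0.5 | 10% | 0.1001 | 0.1140 | 0.1210 | 0.1112 |
| 0.5 | 20% | 0.0969 | 0.1265 | 0.1437 | 0.1202 |
| 0.7 | 5% | 0.0811 | 0.0863 | 0.0888 | 0.0862 |
| 0.7 | 10% | 0.0798 | 0.0905 | 0.0959 | 0.0875 |
| 0.7 | 20% | 0.0772 | 0.1000 | 0.1132 | 0.0945 |

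As more data go missing, the median-fill standard error falls, to below the complete-data value, while the true spread rises. At correlation 0.5 and 20% missing the shortfall is 1 - 0.0969/0.1202 = 19.4%. Over all scenarios it is 3.9-6.0%, 7.6-10.1% and 16.5-19.4%.

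**Rejection of true nulls at nominal 5%** (Monte Carlo error 0.2-0.3 points).

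| Missing | Median fill | Pooled, joint prior | Pooled, per-visit prior |
|---|---|---|---|
| 5% | 5.9-6.5% | 4.4-5.1% | 3.7-4.5% |
| 10% | 6.7-7.6% | 4.2-4.7% | 3.2-3.6% |
| 20% | 10.1-11.3% | 4.0-4.8% | 2.1-2.5% |

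Sensitivity Analysis 5 (no imputation) rejected 4.8-5.5% in the same runs. Mean ANCOVA estimates from median fill and pooling agreed within 0.0001 log units; within a single trial they differed by 0.001-0.004 on average.

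**Second simulation.** Separately written code, with correlation 0.3 or 0.6, random dropout and per-visit regression imputation, gave median-fill rejection of 6.2-7.1%, 7.2-9.1% and 11.2-12.9% at 5%, 10% and 20% dropout. Pooling gave 1.8-4.5%.

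**The case against.** The strongest reply is that the inference rule is already explicit. The paragraph after the median clause fits 100 models, combines them and takes the interval and p-value from the combination. On that reading, the purpose phrase belongs to the 100 datasets, the median only supplies a by-patient value for something like the waterfall plot, and every sentence has a function. No sentence actually says to run the ANCOVA on median-filled data. This is a fair reading and probably the intended one, which is why the harm is conditional. It does not remove the conflict: the median clause sits in the sentence about estimating the treatment effect, no text limits it to displays, and the sample SAS code (one PROC MIXED run with no step by imputation) fits either reading.

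Other points stand in part:
- The missing rates are assumed. Wide windows for the primary time point (days 156-183 or 156-190, SAP Appendix A) and the use of unscheduled fasting records (SAP Table 2) should keep missingness down, so the 20% case may never arise.
- The SAP specifies a joint normal model, so the per-visit prior overstates how conservative pooling would be. The median-fill error rates hardly depend on the prior.
- The consequences are limited. Protocol 10.1.4 bases dose selection on a clinically meaningful effect and safety, and Sensitivity Analyses 5 and 6 use no imputation. At the upper predicted reduction of 64% (protocol 2.4), ln(0.36) = -1.02, and 1.02/0.1437 is about 7 standard errors, so significance would not change.
- Only the ANCOVA was simulated. For the responder models the estimate itself could move: a patient whose predictive median lies just above 100 mg/dL counts as 0 under median fill but about 0.5 on average over imputations, so two such patients in 20 shift the rate by 2 x 0.5/20 = 5 points.

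**Conclusion.** The concern holds in conditional form. SAP 3.3.2 states two rules that cannot both govern the primary inference, and neither document says which does. If the combined fits govern, standard errors are not too small. If the median governs, the nominal 5% test runs at roughly 6%, 7% and 10-11% with 1, 2 or 4 of 20 endpoints missing per arm, under the assumed SD, correlations and completely random missingness. The damage is to standard errors, intervals and p-values; for the ANCOVA the point estimate is practically unaffected. The effect on dose selection is likely to be small, but this is the primary analysis and the ambiguity should be removed before unblinding.

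**What to change.** Delete the median clause from SAP 3.3.2, or confine it to by-patient displays such as the waterfall plot. State that inference for the primary analysis, Sensitivity Analyses 1 and 4, the subgroup analyses and the triglyceride responder models combines the 100 fits by Rubin's rules with small-sample degrees of freedom. As a separate, minor clarification, give Sensitivity Analyses 2 and 3 their own combining rule for the Wilcoxon test and the Hodges-Lehmann estimate.

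This costs one or two sentences and changes no primary result if pooling was always intended. Compared with median fill, intervals widen by 5-7%, 10-14% and 22-31% at 5%, 10% and 20% missing under the joint prior, and by 8-10%, 16-21% and 37-49% under the per-visit prior. Power at a 30% reduction (log ratio -0.357) with correlation 0.5 goes from 92% to 89-90%, from 92% to 84-88%, and from 90-91% to 71-82% across both priors. With correlation 0.7 it goes from 99% to 98%, from 99% to 97-98%, and from 97-98% to 91-95%. Part of the median-fill power comes from its inflated error rate, and pooling is somewhat conservative with 20 patients per arm.

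The documents do not show whether unblinding has taken place. If it has, the study report should say which rule was used; the SAP introduction already requires deviations to be documented there.

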3.3.4 Subgroup Analyses of Primary Endpoint

Subgroup analyses (with log-transformation and imputation method) for the primary endpoint are planned as follow:

- Gender: Male, Female
- Age: <65 and \geq 65 years old
- CV history: established CVD (All patients enrolled in original protocol and protocol amendment 1, and Patients enrolled in protocol amendment 2 per Inclusion Criteria 3a), at risk for CVD (Patients enrolled in protocol amendment 2 per Inclusion Criteria 3b)

- Concomitant drugs used in diabetes: yes, no (ATC code: A10, ATC2 text: Drugs Used in Diabetes)
- Concomitant use of insulin and insulin analogues: yes, no (ATC code: A10A, ATC3 text: Insulins and Analogues)
- Concomitant use of triglyceride lowering drugs (fibrates, omega-3 fatty acids): yes, no to include ATC code: C10AB, ATC4 text: Fibrates, and ATC code: C10AX, ATC4 Text: Other Lipid Modifying Agents, Preferred Term: EICOSAPENTAENOIC ACID ETHYL ESTER, FISH OIL, FISH OIL;OMEGA-3 FATTY ACIDS, FISH OIL;TOCOPHEROL, OMEGA-3 FATTY ACIDS, OMEGA-3-ACID ETHYL ESTER.

